The preregistered plan was to randomly assign participants to different groups through April 2021 (6 months from the start of the intervention; April mailers were sent on April 6, 2021). However, data have not yet been viewed or analyzed as of the uploading of this document. Therefore, random assignment continued past April 2021 and will continue until results inform a decision regarding which version should be sent to all participants. Data until April 2021 will be pulled and examined for the primary analysis. Data past April 2021 may be examined in exploratory analyses.

Statistical Analysis Plan

As of the writing of this plan, all mailers have been sent and the data have not yet been examined.

Primary Research Question: Which mailer version leads to more mammograms?

H1a: Compared to V1, V2 will lead to more mammograms at 6 months.

H1b: Compared to V1, V3 will lead to more mammograms at 6 months.

The researchers do not have a hypothesis on whether sending enhanced versions with or without socks (V2 and V3) would lead to more mammograms.

For these analyses, a logistic regression will be used, using the following model: Outcome ~ Condition. In the model, V2 and V3 will be entered as predictors with V1 as the reference group. For all tests, two-tailed p-values < 0.05 were used to determine statistical significance.

Secondary Research Question 1: Which mailer version leads to greater improvements in health-related outcomes?

H2a: Compared to V1, V2 will lead to more PCP visits, OB-GYN visits (both as proxies for engagement with the health system), and less emergency department visits (less acute issues) at 6 months.

H2b: Compared to V1, V3 will lead to more PCP visits, OB-GYN visits (both as proxies for engagement with the health system), and less emergency department visits (less acute issues) at 6 months.

The researchers do not have a hypothesis on whether sending enhanced versions with or without socks (V2 and V3) would lead to better health-related outcomes.

For these outcomes, regression models with a log-link function and negative binomial distribution will be used (accounting for positively skewed count or count-related data). If the negative binomial models fail to converge or fit appropriately, a Poisson distribution or another model appropriate for the outcome data will be used instead.

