The following basic model will be used for the above analyses: Outcome ~ Condition. For each outcome, V2 and V3 will be entered as predictors with V1 as the reference group. For all tests, two-tailed p-values < 0.05 were used to determine statistical significance.

Secondary Research Question 2: Which mailer version leads to more mammograms and greater improvements in health-related outcomes in the long term (12 months)?

H3a: Compared to V1, V2 will lead to more mammograms, PCP visits, OB-GYN visits (both as proxies for engagement with the health system), and less emergency department visits (less acute issues) at 12 months.

H3b: Compared to V1, V3 will lead to more mammograms, PCP visits, OB-GYN visits (both as proxies for engagement with the health system), and less emergency department visits (less acute issues) at 12 months.

The researchers do not have a hypothesis on whether sending enhanced versions with or without socks (V2 and V3) would lead to better health-related outcomes.

For the mammograms, a logistic regression will be used. For the PCP visits, OB-GYN visits, and emergency department visits, regression models with a log-link function and negative binomial distribution will be used (accounting for positively skewed count or count-related data). If the negative binomial models fail to converge or fit appropriately, a Poisson distribution or another model appropriate for the outcome data will be used instead.

The following basic model will be used for the above analyses: $\text{Outcome} \sim \text{Condition}$. For each outcome, V2 and V3 will be entered as predictors with V1 as the reference group. For all tests, two-tailed p-values < 0.05 were used to determine statistical significance.

Exploratory Research Question: Which mailer version leads to greater improvements in health-related outcomes over time?

H4a: Compared to V1, V2 will lead to a greater increase over time of PCP visits, OB-GYN visits (both as proxies for engagement with the health system), and decrease over time emergency department visits (less acute issues) in the 12 months after the intervention date compared to 12 months before the intervention date.

H4b: Compared to V1, V3 will lead to a greater increase over time of PCP visits, OB-GYN visits (both as proxies for engagement with the health system), and decrease over time emergency department visits (less acute issues) in the 12 months after the intervention date compared to 12 months before the intervention date.

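### A Poisson fallback without robust standard errors could push the secondary visit-count tests above their nominal 5% if the negative binomial is dropped for poor fit

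*Combined protocol and SAP*

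**What the plan says.** Under Secondary Research Question 1 (6 months) and Secondary Research Question 2 (12 months) of the Statistical Analysis Plan, the three visit counts are analysed by log-link negative binomial regression. The reason given is "accounting for positively skewed count or count-related data".

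Both sections carry the same fallback. Should these models "fail to converge or fit appropriately, a Poisson distribution or another model appropriate for the outcome data will be used instead".

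The model contains mailer condition only: "The following basic model will be used for the above analyses: Outcome ~ Condition". V2 and V3 are each compared with V1. There are no covariates and, unlike in the exploratory analysis, no random effect. Each test stands alone: "two-tailed p-values < 0.05 were used to determine statistical significance".

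The documents do not mention robust or sandwich standard errors, quasi-Poisson scaling, an overdispersion check or a criterion for adequate fit. They do not say that the fit of a Poisson fallback would be checked.

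**The concern.** One fallback serves two different failures.

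- **Non-convergence with little overdispersion.** The dispersion estimate sits at its boundary, the counts are close to Poisson, and a Poisson model is sound.
- **Convergence with poor fit.** If the counts are overdispersed in a way the negative binomial does not capture, such as excess zeros or a heavy tail, moving to Poisson cannot help. Poisson is the negative binomial with its dispersion set to zero, so it fits no better and drops the term that allowed for extra variance. With condition as the only predictor, nothing else in the model absorbs that variance.

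In the second case, Poisson with model-based standard errors gives standard errors that are too small. Confidence intervals would be too narrow, and a chance difference between mailers could be reported as an effect on engagement (PCP or OB-GYN visits) or on acute care (emergency department visits).

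**Working it through.** **Inputs from the documents.** Two-sided 5% per test, so the critical value is 1.96. Three count outcomes, two contrasts (V2 and V3 against V1) and two time points give 3 × 2 × 2 = 12 tests, from 3 × 2 = 6 models. The documents state no sample size, visit rate or dispersion, so there is no figure of the plan's own to reproduce. Every dispersion, mean and arm size below is an assumption.

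**Step 1: formula.** Let φ be the variance/mean ratio. Poisson model-based standard errors assume φ = 1, so they are too small by a factor √φ. The true error of the nominal 5% test is 2 × [1 − Φ(1.96/√φ)]. Coverage of the nominal 95% interval is 1 minus that, and interval width relative to the correct width is 1/√φ.

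| Assumed φ | 1.96/√φ | True error | Coverage | Relative width |
|---|---|---|---|---|
| 1.0 | 1.960 | 5.0% | 95.0% | 100% |
| 1.5 | 1.600 | 11.0% | 89.0% | 82% |
| 2 | 1.386 | 16.6% | 83.4% | 71% |
| 3 | 1.132 | 25.8% | 74.2% | 58% |
| 4 | 0.980 | 32.7% | 67.3% | 50% |

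A separate simulation (6,000 trials per scenario, 200 and 500 per arm) agreed with the formula: about 11% at φ = 1.5, 16–17% at 2 and 25–26% at 3. Sandwich standard errors on the same fits gave 4.6–5.4% throughout.

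**Step 2: the poor-fit trigger.** Three-arm null trials were simulated, 4,000 per cell, at 300 and 800 per arm. A negative binomial was fitted and tested with a pooled grouped chi-square fit test. Trials in which it converged but failed that test were kept, a Poisson model was adopted, and V2 was tested against V1. Figures are for 300 / 800 per arm.

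| Assumed counts | φ | Trials flagged | Error, model-based | Error, sandwich |
|---|---|---|---|---|
| 50% structural zeros, otherwise Poisson mean 3 | 2.5 | 4,000 / 4,000 | 22.4% / 22.3% | 5.0% / 5.4% |
| 40% structural zeros, otherwise negative binomial mean 2.5, size 1.5 | 3.7 | 3,820 / 4,000 | 30.0% / 30.8% | 5.1% / 5.3% |
| Poisson-lognormal, mean 1, log-SD 1 | 2.7 | 1,779 / 3,723 | 23.1% / 23.3% | 5.5% / 5.0% |

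The formula in Step 1 gives 21.5%, 30.6% and 23.4% for these three values of φ (2.5, 3.67 and 2.72 before rounding), so the two approaches agree. How often trials are flagged depends on the fit test chosen.

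**Step 3: would a fit check catch it?** The same fit test was applied to the Poisson model in every flagged trial. It failed in 4,000 + 4,000 + 3,820 + 4,000 + 1,779 + 3,723 = 21,322 of 21,322. A consistently applied fit check would therefore avoid the problem.

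**Step 4: the non-convergence trigger.** With truly Poisson counts (means 1.5 and 0.3), the dispersion estimate went to its boundary in 52–54% of trials. Poisson with model-based errors then had an error of 5.0–5.8%, so there is no material problem on this branch. None of the overdispersed trials reached the boundary.

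**Step 5: cost of robust errors when counts are truly Poisson** (40,000 trials per cell; rate ratios assumed for power).

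| Mean, n per arm | Error, model-based / sandwich | Power, model-based / sandwich (rate ratio) |
|---|---|---|
| 1.5, 300 | 5.04% / 5.09% | 83.5% / 83.6% (1.21) |
| 1.5, 800 | 5.10% / 5.15% | 82.3% / 82.4% (1.12) |
| 0.3, 300 | 4.99% / 5.08% | 87.3% / 87.3% (1.52) |
| 0.3, 800 | 4.95% / 5.01% | 84.7% / 84.7% (1.29) |

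**The case against.** The strongest reply is that the clause already points the right way. Its wording can be read as making appropriateness to the data the test for any replacement model: Poisson for a negative binomial at its dispersion boundary, something else for excess zeros or heavy tails. An analyst who has just rejected the negative binomial on fit is unlikely to stop checking and adopt a nested model that fits worse, and Step 3 shows that a second check would catch it. Poor fit can also come from under-dispersed counts, where Poisson errs on the safe side: about 1.3% error at an assumed ratio of 0.6. And the plan's silence on the variance estimator is not a decision to use model-based errors.

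Most of this stands as a limit on likelihood. Harm needs four things together: rejection of the negative binomial for poor fit to overdispersed counts, choice of Poisson over another model, no check of its fit, and model-based standard errors. Twelve tests is a ceiling, reached only if all six models go that way. The percentages are properties of assumed distributions, not forecasts for this trial.

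It does not remove the point. Poisson is the only fallback named, it is permitted on the poor-fit trigger, no rule decides between it and an alternative, and no fit check is required of it.

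It is also fair to say that the missing fit criterion and the missing rule for choosing a model are a wider looseness. Robust errors do not settle which model is chosen, but they protect the tests if the choice is Poisson.

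**Conclusion.** The concern holds, as a minor one. If the negative binomial is set aside for poor fit to overdispersed counts and Poisson is used with model-based standard errors, the secondary visit-count tests run well above 5%: about 11% to 33% for assumed variance/mean ratios of 1.5 to 4, and 22% to 31% in the simulated poor-fit scenarios. The probability of reaching that situation cannot be computed from the documents. If the fallback is triggered by little overdispersion, there is no problem. The logistic analysis of mammogram completion is unaffected, and the exploratory random-intercept model has not been shown to be affected.

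**What to change.** Add one sentence after the fallback clause under Secondary Research Question 1 and again under Secondary Research Question 2:

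> *If a Poisson model is used, robust (sandwich) standard errors will be used for tests and confidence intervals.*

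This keeps the rate ratio as the effect measure and holds the error near 5% under either trigger, whether or not the Poisson fit is checked. The option of another suitable model and the exploratory analysis can stay as written.

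The cost is one sentence in two places and one software option. With truly Poisson counts, the standard errors become slightly more variable (the ratio of sandwich to model-based has an SD of 1.8–2.9% at 300–800 per arm), and power changes by no more than about 0.1 percentage point. The plan, dated June 11, 2021, states that "all mailers have been sent and the data have not yet been examined". If that is still so, the sentence can be added before any results are seen. If not, it should be recorded as a later addition.

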Evaluation of Mailers Promoting Mammogram Screening
(NCT04555902)

Study Protocol with Statistical Analysis Plan

June 11, 2021

Study Protocol

Purpose

The purpose of this study is to evaluate, prospectively, the potential impact of different mailer conditions (standard content including a free gift, content designed with behavior science, content designed with behavior science including a free gift) on mammogram screening.

Introduction

Mammogram screening for women, starting at age 50, can significantly reduce the risk of complications due to breast cancer. As part of an existing outreach campaign, the health system mails a postcard and small gift (pink socks) to women on the month of their 50th and 64th birthdays to promote annual mammogram screening.

The researchers are evaluating two new versions of the mailers against a standard mailer to see which version leads to greater uptake in mammograms. The new mailers had content that applied behavioral nudge theory - specifically, loss frames and fear appeals - to encourage taking action. One of the two new versions did not include the small gift, to test whether its inclusion or exclusion has any effect on mammogram screening.

Methods

Sample

Female Geisinger Health Plan members turning age 50 and 64 in that month were included in the study. Although the intervention began in October, women with birthdays as early as June 2020 were included. These additional participants were included because the mailer program was paused from June to October 2020 due to the COVID-19 pandemic; the October mailing was meant to contact all the eligible women who were not contacted since June.

Experimental conditions

All participants received a two-sided, 9x6 postcard that had a picture and attention-grabbing slogan in the front. The back of the postcard included a brief, persuasive message, with a toll-free number that could be used for scheduling a mammogram. Participants were randomly assigned to receive one of the three versions of mailers detailed below.

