Standard Version with Socks (V1): The picture in front showed a woman posing against a pink background. The slogan in front said, “It’s time to think pink” and the back of the postcard mentioned that staying healthy benefited the recipient and their loved ones. It encouraged recipients to get their annual mammogram and show they are “part of the fight against breast cancer” by putting on some cute pink socks. This postcard and a pair of pink socks were sent together in a larger envelope.

Enhanced Version without Socks (V2): The picture in front showed two women with pink- and grey-colored clothing jogging together. The slogan in front said, “To do: Lower my risk of breast cancer.” The back of the postcard framed an annual mammogram as the best way to find and beat breast cancer, with late detection leading to more costs, less effective treatments, and lower chances of recovery. Like the standard version, it mentioned that staying healthy benefited the recipient and their loved ones. This version was not accompanied by socks and was not sent in an envelope.

Enhanced Version with Socks (V3): This postcard was identical to V2, with the exception of an additional message at end, which asked recipients to accept the socks as a small gift and reminder to take care of their health. This postcard and a pair of pink socks were sent together in a larger envelope.

Outcome measures

The primary outcome measure was mammogram completion (yes/no) 6 months from the intervention date.

The secondary outcome measures were mammogram completion at 12 months (yes/no), primary care provider (PCP) visits (count) at 6 and 12 months, Obstetrician-Gynecologist (OB-GYN) visits (count) at 6 and 12 months, breast cancer diagnosis (lab notes) at 6 and 12 months, and emergency department visits (count) at 6 and 12 months.

Exploratory outcome measures were mammogram completion, primary care provider visits, breast cancer diagnosis, and emergency department visits in 2019.

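### The H2 and H3 visit-count models leave out the pre-mailing visit count that H4 already needs: a minor loss of precision on secondary outcomes, not a bias

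*Combined protocol and SAP*

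**What the plan says.** Under Secondary Research Question 1 (H2, 6 months), the SAP says of PCP, OB-GYN and emergency department visits: "For these outcomes, regression models with a log-link function and negative binomial distribution will be used". The predictors are then fixed: "The following basic model will be used for the above analyses: Outcome ~ Condition", with V2 and V3 entered against V1. Secondary Research Question 2 (H3, 12 months) does the same: "For the PCP visits, OB-GYN visits, and emergency department visits, regression models with a log-link function and negative binomial distribution will be used", again with condition alone. If the negative binomial model fails, a Poisson or other model may replace it. No baseline covariate is named in either place.

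The Exploratory Research Question (H4a, H4b) compares the same three visit types "in the 12 months after the intervention date compared to 12 months before the intervention date". The pre-mailing counts therefore have to be extracted in any case. This requirement comes from the wording of the hypotheses; the H4 formula itself has no period term, which is a separate matter.

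The protocol's Outcome measures section describes the earlier period differently: "Exploratory outcome measures were mammogram completion, primary care provider visits, breast cancer diagnosis, and emergency department visits in 2019". That list uses a calendar year and does not include OB-GYN visits.

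On timing, the SAP states that "all mailers have been sent and the data have not yet been examined".

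**The concern.** A woman's earlier visits of a given type are often a good predictor of her later visits of that type. When that is so, a model with condition alone leaves predictable between-woman variation in the error term, and the H2 and H3 rate ratios get wider confidence intervals than the same data pull could give. The covariate is measured before mailing, so the mailer cannot have affected it, and H4 needs it anyway.

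What is at stake is the precision of the V2 and V3 comparisons on three secondary visit counts at two time points. The primary mammogram result is not touched.

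**Working it through.** **No figure to reproduce.** The documents state no sample size, power, effect size, visit rate or dispersion for these outcomes. Every input below is assumed.

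**Inputs.** μ is the mean count in the follow-up window (6 or 12 months), μ₀ the mean count in the 12 months before mailing, and k the negative binomial dispersion (variance = μ + kμ²). Pre/post correlation is that of the women's underlying log rates.

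**Best case in closed form.** Suppose each woman's rate is gamma-distributed and does not change. Near the null, the variance of the log rate ratio is proportional to 1/μ + k unadjusted and to 1/μ + 1/(1/k + μ₀) adjusted. The arm sizes cancel, so

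variance ratio = [1/μ + 1/(1/k + μ₀)] / [1/μ + k].

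With equal 12-month windows this is (1 + 2x)/(1 + x)², where x = kμ.

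- μ = 3, k = 0.5: (0.333 + 0.200)/(0.333 + 0.500) = 0.64.
- μ = 0.3, k = 5: (3.333 + 2.000)/(3.333 + 5.000) = 0.64.
- Both have x = 1.5, and 4/6.25 = 0.64.
- μ = 0.3, k = 1: (3.333 + 0.769)/(3.333 + 1.000) = 0.95.

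The gain therefore depends on dispersion times mean, not on frequency alone.

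**Less stable rates.** The two right-hand columns come from simulation: log-normal rates, three arms of 500, 200 runs per setting, negative binomial fits with and without log(1 + pre count). Entries are variance ratios (adjusted/unadjusted) at 6 / 12 months. The simulated ones use median model-based standard errors.

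| 12-month mean | k | Fully stable (closed form) | Correlation 0.8 | Correlation 0.5 |
|---|---|---|---|---|
| 3 | 0.5 | 0.74 / 0.64 | 0.87 / 0.82 | 0.95 / 0.94 |
| 3 | 1 | 0.55 / 0.44 | 0.80 / 0.74 | 0.93 / 0.91 |
| 0.3 | 1 | 0.97 / 0.95 | 0.98 / 0.97 | 1.00 / 0.99 |
| 0.3 | 2 | 0.91 / 0.86 | 0.96 / 0.94 | 0.99 / 0.98 |
| 0.3 | 5 | 0.74 / 0.64 | 0.92 / 0.88 | 0.98 / 0.97 |

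The variance of the estimates across only 200 runs is too noisy to use at k = 5 (ratios of 1.01 and 0.76 at correlation 0.8), so that row rests on the model-based figures.

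**Large-sample check.** With 60,000 women per arm, log-normal rates, k = 0.8 and adjustment for the pre-mailing count only, the robust variance fell by:

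- 17% at 3 visits a year, correlation 0.6, 12 months (observed count correlation 0.37);
- 13.5% for the same at 6 months;
- 4% at 3 a year, correlation 0.3;
- 6.5% at 1 a year, correlation 0.6;
- 1% at 0.3 a year, correlation 0.6.

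A 17% fall multiplies the standard error by √0.83 = 0.91 and is worth about 1/0.83 = 1.20 times as many women. In a separate large-sample run at correlation 0 the change was 0.0%.

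**Bias check.** At a true log rate ratio of 0.131 (4,000 replicates, 800 per arm), the mean estimate was 0.1305 unadjusted and 0.1300 adjusted with log-normal rates, and 0.1311 and 0.1309 with gamma rates. Those adjusted fits also included age cohort and mailing. The target is the same and neither model is biased.

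**Reasons the correlation may be low.** The protocol says "the mailer program was paused from June to October 2020 due to the COVID-19 pandemic". The 12 months before every mailing from October 2020 to April 2021 include June to September 2020. If visits were disrupted then too, which the documents do not say, earlier counts would predict later ones less well. The SAP also says that a mammogram in the prior 12 months was part of the exclusion criteria; selecting on low recent screening could compress the earlier PCP and OB-GYN counts.

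**The case against.** The strongest reply is that nothing here is an error. A prespecified, simple comparison of randomised groups is legitimate, the outcomes are secondary, and the plan makes no power claim that could fail. This stands, and it is why the point is minor. It does not remove the point, since the covariate is already needed for H4 and can be added without changing what is estimated.

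A second reply is that the benefit is unproven. This also stands: the documents do not show whether any of the three visit types would gain noticeably.

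A third is that calendar 2019 predates the pandemic pause and might predict later visits better. The documents cannot settle this. H4's window has the advantage that the SAP already asks for it for all three visit types.

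A reader might infer more than the documents support:

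- **That the unadjusted rate ratios are biased or the tests invalid.** Randomisation and the log link rule this out, as the bias check shows.
- **That only frequent visits matter.** Mean 0.3 with k = 5 has the same best-case ratio as mean 3 with k = 0.5. Conversely, at mean 3 and correlation 0.5 the model-based gain is only 5 to 9%.
- **That age cohort and mailing month should be added too**, since eligibility reveals both ("Female Geisinger Health Plan members turning age 50 and 64 in that month were included in the study"). With an assumed age log rate ratio of 0.2 and equal cohorts, the explained variance is (0.2/2)² = 0.01. Against 1/3 + 0.8 = 1.13 that is 0.9%; against 1/0.3 + 0.8 = 4.13 it is 0.2%. No separate gain was shown for month, and seven mailings would add six parameters to models that the SAP already expects may not converge.
- **That robust standard errors are needed.** Simulated type I error of the unadjusted model with model-based errors was 5.3 to 6.8% with log-normal rates and 5.1 to 5.6% with gamma rates. This turns on an assumed distribution and is a separate question from the missing covariate.

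**Conclusion.** The point holds as a minor, free improvement. The H2 and H3 visit-count models omit a pre-mailing count that the plan needs for H4, and the price is some precision on secondary outcomes.

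Its size cannot be derived from the documents. Under the assumptions above, at correlations of 0.5 to 0.8, the model-based variance reduction is 5 to 26% at 3 visits a year (k 0.5 to 1), 0 to 6% at 0.3 a year with k 1 to 2, and 2 to 12% at 0.3 a year with k = 5. The gain is likely larger for frequent or strongly overdispersed visits with a stable pre/post pattern, and could be near zero if the correlation is weak. The direction and the absence of bias rest on randomisation alone; the percentages rest on assumed rates, dispersions and correlations. The 6- and 12-month mammogram models are outside this point.

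**What to change.** Before the data are viewed:

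1. Add log(1 + the same outcome's count in the 12 months before the intervention date) to the H2 and H3 models for PCP, OB-GYN and emergency department visits.
2. Carry the same term into any Poisson or other fallback model.
3. Keep Outcome ~ Condition as a sensitivity analysis.
4. Use H4's 12-month window for all three visit types, and reconcile the Outcome measures section with it, since that section refers to 2019 and leaves out OB-GYN visits.
5. Leave the mammogram logistic models unchanged.

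The cost is a few lines of SAP text and slightly more analysis. No extra extraction is needed beyond H4's. The plan should say how women without a complete prior year of records are counted, a question that H4 raises anyway. The downside is that the gain may turn out negligible. Fixing the covariate now also avoids the appearance of choosing it after seeing results.

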The researchers do not have a hypothesis on whether sending enhanced versions with or without socks (V2 and V3) would lead to better health-related outcomes.

While the number of mammograms 12 months before the intervention was included as an outcome in the Clinical Trials record, this will no longer be analyzed, as having mammograms in this time period was part of the exclusion criteria. The preregistration of this outcome at this particular time period was done in error.

For the PCP visits, OB-GYN visits, and emergency department visits, mixed-effects regression models with a log-link function and negative binomial distribution will be used (accounting for positively skewed count or count-related data). If the negative binomial models fail to converge or fit appropriately, a Poisson distribution or another model appropriate for the outcome data will be used instead.

The following random intercepts model will be used for the above analyses: $\text{Outcome} \sim \text{Condition} + (1| \text{Participant})$. For each outcome, V2 and V3 will be entered as predictors with V1 as the reference group. For all tests, two-tailed p-values < 0.05 will be used to determine statistical significance.

Examination of Additional Outcomes

Only descriptive statistics will be reported for breast cancer diagnoses at 6 and 12 months. These will be used to illustrate how many people detected breast cancer due to the program and to estimate the costs to the hospital system.

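### The exploratory H4 model has no Period or Condition-by-Period term, so no coefficient in it estimates the between-arm difference in change that H4a and H4b state

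*Combined protocol and SAP*

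**What the plan says.** Under Exploratory Research Question, H4a states that, relative to V1, "V2 will lead to a greater increase over time of PCP visits, OB-GYN visits", together with a decrease in emergency department (ED) visits. The comparison is between visits "in the 12 months after the intervention date compared to 12 months before the intervention date". H4b says the same for V3.

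The model for these hypotheses is introduced by "The following random intercepts model will be used for the above analyses". It is a negative binomial mixed model with log link, `Outcome ~ Condition + (1|Participant)`, with V2 and V3 as the named predictors and V1 as reference. The section does not say which rows enter. A Poisson or other model may be substituted, but only if the negative binomial model does not converge or fit.

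For the 12-month hypotheses H3a and H3b (Secondary Research Question 2), the SAP writes "The following basic model will be used for the above analyses" and gives `Outcome ~ Condition`, without a participant intercept.

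The Outcome measures section describes the exploratory measures differently: "Exploratory outcome measures were mammogram completion, primary care provider visits, breast cancer diagnosis, and emergency department visits in 2019".

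**The concern.** H4 is a hypothesis about change: the post/pre ratio in V2 or V3 divided by the post/pre ratio in V1. On a log-link model with two rows per participant, that quantity is the Condition-by-Period interaction. The stated model has no interaction, Period term, baseline covariate or change score. An analyst who follows it literally would report the Condition coefficient as a greater change over time, which it does not measure.

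A Period main effect is needed as well. With an interaction but no main effect, V1 would be forced to show no change, and any change common to all arms would be loaded onto V2 and V3. Such a change is plausible. Women were selected on the pre-mailing year, since "having mammograms in this time period was part of the exclusion criteria", and that year overlaps the period when "the mailer program was paused from June to October 2020 due to the COVID-19 pandemic". The documents give no visit volumes, so this shows only that pre and post rates may differ.

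**Working it through.** The plan gives no sample size, visit rate or effect size for H4, so it has no figure to reproduce. The check is of what the stated model estimates.

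**Possible readings of the formula**

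- *Pre and post rows stacked.* This is the likeliest, because a participant intercept appears here and not in the post-only H3 model. Condition is then the arm contrast averaged over both years.
- *Post rows only.* There is one row per participant, the intercept is hard to separate from negative binomial overdispersion, and the contrast is that of H3.
- *Change score as outcome.* This is not stated, and a change can be negative, which a log-link count model cannot take.

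**Size on the stacked reading**

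Let RR be the true ratio of change against V1 and c the pre/post rate ratio in V1. Randomisation makes pre-mailing rates equal in expectation. With the V1 post rate set to 1, the two-year total is c + 1 in V1 and c + RR in the comparison arm, so

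Condition ratio = (c + RR)/(c + 1); share of log effect retained = ln[(c + RR)/(c + 1)] / ln(RR).

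For example, RR = 1.20 and c = 0.8 give 2.0/1.8 = 1.111, and 0.1054/0.1823 = 58%. Both c and RR are assumptions.

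| c | RR 1.20 becomes | share kept | RR 0.80 becomes | share kept |
|---|---|---|---|---|
| 0.6 | 1.125 | 65% | 0.875 | 60% |
| 0.8 | 1.111 | 58% | 0.889 | 53% |
| 1.0 | 1.100 | 52% | 0.900 | 47% |
| 1.2 | 1.091 | 48% | 0.909 | 43% |

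**Fitting the stated model**

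The closed form is a pooled marginal ratio, so the negative binomial random-intercept model was also fitted to very large simulated data (1.5 million per arm; assumed post mean 1.5, intercept variance 0.7, period-level gamma variance 0.3).

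- RR 1.20 at c = 0.6, 0.8, 1.0, 1.2: Condition-only gave 1.121, 1.109, 1.100, 1.090. The interaction gave 1.200, 1.198, 1.200, 1.201.
- RR 0.80 at c = 1.0: 0.902 against 0.800.
- Weak pre/post correlation, c = 0.8, RR 1.20: 1.110 against 1.203.

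**Type I error and power**

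Settings assumed: 500 per arm, post mean 1.5, c = 0.8; 4,000 simulated trials each; robust tests on log ratios of arm means. Null rejection was 4.8% to 5.9% for Condition-only and 5.0% to 5.6% for the interaction. A small check of the stated mixed model itself (150 replicates per setting) gave 3% to 6%. Power at RR 1.20:

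| Pre/post correlation | Condition-only | Interaction | Post-only (H3) |
|---|---|---|---|
| 0.57 | 30% | 67% | 62% |
| 0.38 | 29% | 45% | 54% |
| 0.23 | 31% | 37% | 53% |
| 0.09 | 36% | 32% | 53% |

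The post-only column uses approximate (delta-method) variances. In a separate simulation of the same four settings, the post count adjusted for the pre count had 79%, 62%, 54% and 54% power, against 66%, 46%, 34% and 31% for the interaction.

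**Pre-mailing window**

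Outcome measures uses calendar 2019. If mailers went out on the 1st of the month, the 12 months before mailing contain 92, 61 and 31 days of 2019 for October, November and December 2020, and none for January to April 2021. That section also omits OB-GYN visits, which H4 includes, and lists mammogram completion, although the SAP drops the pre-mailing mammogram outcome.

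**The case against.** The strongest reply is that little is lost. Under randomisation the pre-mailing rates are equal in expectation, so the ratio of changes equals the 12-month post-only rate ratio. H3 already estimates that ratio, undiluted, for all three visit types. The dilution exists only on the stacked reading, and the SAP does not say which rows enter. The interaction is also less powerful than the planned H3 contrast in three of the four settings above. Every magnitude rests on assumed rates, the question is exploratory, and the formula may be shorthand.

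Most of this is fair and limits the importance of the point. H3 does protect the substantive 12-month conclusion, the interaction is not offered as a gain in power, and the sizes are illustrative. None of it makes the stated model answer H4. On the post-only reading H4 adds nothing to H3; on the stacked reading the coefficient is a different, diluted quantity. The shorthand explanation is hard to sustain when the predictors are listed explicitly, and the fallback clause would not add a time term.

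**Conclusion.** The concern holds. As written, the H4 model either averages the arm contrast over a year before any mailer was sent or duplicates H3; in neither case does it fit the change comparison stated in H4a and H4b. On the stacked reading, 48% to 65% of the log effect is retained for a true ratio of 1.20, and 43% to 60% for 0.80, over an assumed c of 0.6 to 1.2. A chance baseline imbalance would also pass into the Condition coefficient, whereas the interaction nets it out. The direction of the dilution does not depend on the assumed values; its size does. False positives are not inflated under randomisation, and the confirmatory and secondary analyses are untouched. It should be fixed because the result would carry the wrong label and the wrong size.

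**What to change.** Replace the H4 model statement with wording such as:

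> Each participant contributes two rows: visits in the 12 months before and in the 12 months after the mailing date. Model: Outcome ~ Condition * Period + (1|Participant), with V1 and the pre-mailing period as references. H4a is tested on V2:Period and H4b on V3:Period, reported as ratios of rate ratios with 95% confidence intervals.

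Optionally add a supporting analysis of the post-mailing count on Condition plus log(1 + pre-mailing count). Baseline adjustment had more power than the interaction in all four settings examined.

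Bring the exploratory list in Outcome measures into line with H4: use the same 12-month pre-mailing window, add OB-GYN visits, and remove the mammogram item that the SAP no longer analyses.

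The cost is SAP wording only, since H4 already requires both counts. The SAP says the data have not been examined. It is dated June 11, 2021 and mailing began in October 2020, so no 12-month follow-up window had closed and the correction could be prespecified cleanly.
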